2.5.2 Safety

[figure not shown]
In CONRAD-146, a study conducted in the US, a single dose of TAF/EVG insert administered vaginally was safe and well-tolerated (manuscript under review).²⁷ There were no product related treatment-emergent adverse events (TEAE). There were 8 TEAEs reported by 7 participants (43.8%). The most common TEAE was increased blood glucose, occurring in 3 (18.8%) participants overall. No other TEAE occurred in more than 1 participant. All TEAEs were mild, and none were related to study treatment. TEAEs considered related to study procedure occurred in 2 (12.5%) participants overall. All events of increased blood glucose and events related to the study procedure occurred in Group 1 (4 hour sample collection) (3 [37.5%] and 2 [25.0%], respectively) and did not occur in Group 2 (24 hour sample collection). No treatment-emergent serious adverse effects (TESAE), deaths or TEAEs led to dose interruption, discontinuation of study treatment, or premature withdrawal from the study.

In CONRAD 134, an open-label study conducted in the US that assessed in-vivo disintegration time, safety, and product acceptability of 4 placebo vaginal inserts in 32 women aged 18-50 who were not at risk of pregnancy, placebo inserts were found to be safe, with one mild AE reported that was subsequently assessed as being unrelated to study drug. The optimized insert prototypes were found to disintegrate faster and have higher acceptability over first generation inserts.^{26, 31}

CONRAD 117, conducted in the US, was the first-in-human study of vaginal microbicide inserts using TFV and/or FTC containing vaginal inserts. TEAEs were minimal; only one TEAE met the pre-specified criterion for the safety endpoint, but this event was in the placebo group. Colposcopy and physical exam findings were minimal, as were changes in microflora and systemic laboratory values.²⁶

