10.2 Study Endpoints

Primary Endpoints

Safety

- Changes after dosing:
 - Any TEAE, Grade 2 or higher

Secondary Endpoints

Pharmacokinetics (PK)

- Concentrations of TFV, TAF and EVG in plasma after dosing
- Concentrations of TFV, TAF and EVG in CVF and RF after dosing
- Concentrations of TFV, TFV-DP, TAF and EVG in CVT after dosing

Modeled *in vitro* PD

- Anti-HIV activity in CVF obtained at baseline and after dosing
- Anti-HSV activity in CVF obtained at baseline and after dosing

Acceptability

- Responses to key questions on acceptability (e.g., satisfaction, comfort with insertion, willingness to use) at enrollment and after dosing

Subclinical Safety and Vaginal Microbiome

- Changes in HIV-1 target immune cell phenotype (e.g., CD45, CD68, CD3, and CD1a) and HIV-1 activation/proliferation markers (e.g., HLA-DR) in CVT
- Changes in soluble markers of innate mucosal immunity and inflammatory response in CVF (e.g., IL-1 α , IL-6, IL-10, TNF α , RANTES, MIP-1 α , IP-10, GM-CSF, IL-8, IL-1RA, SLPI, and BD2)
- Changes in the Nugent Score, relative abundance of vaginal microbial species and community state type (CST) measured by 16S RNA sequencing

Exploratory Endpoints

Modeled Tissue PD

- p24 antigen production in CVT infected with HIV-1 *ex vivo*, at baseline and after dosing

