10.4 Sample Size and Power Calculations

The sample size will be calculated assuming a clinically significant difference between the TAF/EVG insert and placebo of 60% or more. Therefore, the sample size needed to detect such

difference at 5% level of significance and 80% power is 20 (10 participants in each arm) per site for a total of 60 participants to complete. Replacement participants will be enrolled in the event of LTFU.

The sample size estimated above will have enough power to conduct a stratified analysis by study site to show the generalizability of the intervention findings.

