10.5 Randomization Procedures

Participants will be randomized (1:1) to receive either combination TAF/EVG or placebo vaginal insert. Participants will be randomized 1:1:1 to one of three timepoint groups for tissue sample collection post dosing.

Participants	Randomization Group
30	TAG/EVG insert
30	Placebo insert

Sample Collection Groups	Timepoints after Dosing
Timepoint group 1	24 hours (7a)
Timepoint group 2	48 hours (7b)
Timepoint group 3	72 hours (7c)

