10.8.2 Primary Analysis(es)

Product safety will include summaries overall of the incidence of treatment-emergent adverse events, incidence of product-related urogenital adverse events, and incidence of other findings from pelvic examinations (e.g., ulcerations, abrasions, edema, and bleeding). To compare the incidence of TEAEs between the two study arms, Chi-squared test for independence or Fisher's exact test will be used as per the assumptions.

Changes from baseline in clinical laboratory endpoints will be summarized. Shift tables will be produced where relevant.

Evaluation for Study Objectives:

Study objectives will be evaluated by clinical review of descriptive summaries and graphical displays.

Descriptive Statistics:

Categorical variables will be summarized by frequencies and percentages. Continuous variables will be summarized by mean (SD) when found normally distributed. Median (IQR) will be used otherwise. Normality will be assessed graphically by Q-Q plots and statistically by Shapiro-Wilk test for normality. Categorical variables will be summarized by frequency and percentages (e.g. incidence of adverse events).

In addition to descriptive summaries, pharmacokinetic analysis will include time concentration curves for each participant and pooled by sample timepoint group.

To assess for the comparability between the two arms of the study at baseline, t-test or Mann-Whitney test will be used to assess for the differences in continuous variables as appropriate based on the normality assumption. While chi-squared test for independence or Fisher's exact test will be used for categorical variables as appropriate.

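### At low event counts the primary safety comparison falls to Fisher's exact test, which is valid but very conservative; Boschloo's exact test in that branch would be more sensitive to harm, and at 10 v 10 per site would keep the stated 80% power

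*Protocol*

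**What the plan says.** The primary endpoint is binary for each woman: "Any TEAE, Grade 2 or higher" (Protocol 10.2). Section 10.8.2 compares incidence between arms by "Chi-squared test for independence or" Fisher's "exact test will be used as per the assumptions". The condition for switching is not spelled out.

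Section 10.4 plans on a difference between the "TAF/EVG insert and placebo of 60% or more". It states that the number needed to detect such a "difference at 5% level of significance and 80% power is 20 (10 participants in each arm) per site", which makes 60 completers over the three sites, and adds that this is enough for an analysis stratified by site. Allocation is 1:1 (10.5), so the comparison is 30 v 30 pooled and 10 v 10 within a site.

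The protocol gives no expected rate of Grade 2 or higher events. The nearest evidence is the single-dose study of 16 women in section 2.5.2: "All TEAEs were mild, and none were related to study treatment". That is 0 of 16 at Grade 2 or above.

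**The concern.** Choosing chi-squared or Fisher is conventional, and both names are fixed in the protocol. With few events, however, Fisher uses only a small part of its nominal 5%. In an efficacy trial that protects against a false claim. In a safety comparison it works the other way, because the test leans towards reporting no significant difference.

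Two things are at stake. One is sensitivity of the pooled primary comparison to a moderate excess of Grade 2 or higher events when such events are rare. The other is whether the test named in 10.8.2 delivers the 80% power per site that 10.4 states.

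**Working it through.** **Assumptions.** Two-sided 5% test; Fisher used if any expected count is below 5, otherwise uncorrected chi-squared; the 60% in 10.4 read as percentage points. The protocol states none of these.

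**1. The plan's own figure.** With p̄ the mean of the two rates,

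n per arm = [1.96·√(2p̄(1−p̄)) + 0.84·√(p₁(1−p₁)+p₀(1−p₀))]² / 0.60².

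For 80% v 20%: (1.386 + 0.476)² / 0.36 = 9.6, so 10. Control rates of 0 to 40% give 8 to 10, and rates of 10 to 30% give exactly 10. The stated 10 per arm per site is reproduced, by a formula that corresponds to the uncorrected chi-squared test.

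**2. Which test is used.** With t affected women in 30 v 30, the expected number per arm is t/2, which is below 5 when t < 10. The chance of t < 10 is 99.9% at a common rate of 5%, 93% at 10%, 59% at 15% and 21% at 20%. In 10 v 10, both t/2 and (20−t)/2 must reach 5, so every table except those with t = 10 goes to Fisher.

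**3. True size, 30 v 30.** Size at common rate π is the sum, over all rejecting tables, of the product of the two binomial probabilities.

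| Common rate | Planned rule | Chi-squared/Boschloo rule |
|---|---|---|
| 5% | 0.15% | 0.7% |
| 10% | 1.2% | 2.6% |
| 15% | 2.9% | 3.9% |
| Maximum at any rate | 5.2% | 5.2% |

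Fisher alone never exceeds 2.7% and Boschloo alone never exceeds 4.7%. The 5.2% comes from the chi-squared branch, which both rules share.

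**4. Where the rules differ, 30 v 30.** Boschloo's p is the largest probability, over all common rates, of a table with a Fisher p at least as small as the one observed.

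- 5 v 0: Fisher p = 2·C(30,5)/C(60,5) = 2 × 142,506 / 5,461,512 = 0.052; Boschloo p = 0.027.
- 7 v 1: Fisher p = 2·[30·C(30,7)+C(30,8)]/C(60,8) = 2 × 66,926,925 / 2,558,620,845 = 0.052; Boschloo p = 0.027.

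These two splits and their mirror images are the only tables whose verdict changes. No table significant under the planned rule becomes non-significant.

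**5. Power, 30 v 30.** With no placebo events, the planned rule needs 6 active-arm events and the Boschloo rule needs 5. At 15% v 0% this is P(X≥6) = 29% against P(X≥5) = 48%, with X binomial(30, 0.15).

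| Active v placebo | Planned rule | Chi-squared/Boschloo rule |
|---|---|---|
| 15% v 0% | 29% | 48% |
| 20% v 0% | 57% | 74% |
| 20% v 2% | 42% | 56% |
| 20% v 5% | 27% | 36% |
| 30% v 10% | 47% | 49% |
| 35% v 10% | 65% | 66% |

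**6. Power within a site, 10 v 10, at a 60-point difference.**

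| Active v placebo | Planned rule | Boschloo in the low-count branch |
|---|---|---|
| 80% v 20% | 64% | 81% |
| 70% v 10% | 67% | 82% |
| 65% v 5% | 72% | 86% |
| 60% v 0% | 83% | 95% |

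Here the planned rule's size never exceeds 1.3%; with Boschloo the maximum is 4.2%.

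**The case against.** The case for leaving the plan alone is substantial.

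- **Fisher is valid and standard.** This stands. The cost is sensitivity; no error rate is inflated.
- **The low event rate is weakly supported.** This also stands. Zero of 16 has a two-sided exact 95% upper bound of 1 − 0.025^(1/16) = 20.6%, and it comes from a single dose. This trial gives ten doses, with biopsies at three visits. At a 20% common rate the rule would mostly select chi-squared.
- **The pooled gain comes from two borderline splits** and nearly vanishes once the placebo rate is 10% or more. Correct.
- **No decision rests on p < 0.05.** Section 10.8.2 also has the objectives judged by clinical review of the summaries and plots. Under section 8.2 the safety review team can recommend a pause or stop without any significance threshold. A reader might infer that a 5 v 0 or 7 v 1 split would go unnoticed. The documents do not support that: it would be tabulated and reviewed, only with a p-value just above 0.05.
- **The replacement is not perfect.** Boschloo's size is still only 0.7% at a 5% rate, and the combined rule reaches 5.2%, so it is not exact overall. That excess is already in the plan.
- **The switching trigger could be left to the SAP.** True of the trigger, but the two tests are named in the protocol.

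What remains is that replacing only the Fisher branch loses no rejection and leaves the maximum size unchanged in the pooled comparison. The shortfall in per-site power also does not depend on events being rare.

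**Conclusion.** The point holds as a recommendation to improve sensitivity. If Grade 2 or higher events are rare in the placebo arm (0 to 5%), replacing Fisher by Boschloo in the low-count branch adds about 9 to 19 percentage points of power in the scenarios shown. With placebo rates of 10% or more it adds 1 to 2 points.

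Within a site, the named test generally misses the 80% stated in 10.4 (64% to 72%, except at a placebo rate near zero), while Boschloo meets it. A reader might conclude that the sample size of 10 per arm per site is wrong. It is not: the figure follows from the usual formula, and the gap lies between that formula and the test that would be applied. Nor is the pooled comparison short of power for a 60-point difference; Fisher's power there is at least 99.8%.

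All of this rests on a two-sided test, the expected-count trigger and the percentage-point reading of 60%.

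**What to change.** In section 10.8.2, before unblinding, replace Fisher's exact test by Boschloo's unconditional exact test wherever an expected count is below 5, for both the pooled and the per-site comparisons. State that trigger and the two-sided 5% level explicitly. Report an unconditional exact 95% confidence interval for the risk difference beside the clinical review, so that a non-significant result is read with its uncertainty.

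The cost is a change of wording and a small amount of code, with no change to sample size or data collection. The downside is a less familiar test that may need specific software.

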10.8.3 Secondary and Exploratory Analyses

Safety:

To assess for the difference in subclinical safety endpoints between TAF/EVG and placebo group, the incidence of different TEAES will be calculated and risk ratio will be estimated. Chi-squared test or fisher exact test will be used as appropriate. A binary variable will be created for each one of the TEAEs of interest, then Multivariable logistic regression will be used to assess for the difference in the occurrence of TEAEs. In this model the risk ratio will be calculated instead of the odds ratio using Stata command (*oddrisk*).

While for quantitative laboratory safety parameters, mixed-effect design will be used to assess for the changes in these parameters over time within the TAF/EVG and placebo group separately

and will assess for the differences in the laboratory parameters between the TAF/EVG and placebo group.

PK and PD:

PK analysis will include descriptive statistics by sample time point of EVG, TFV, and TAF concentrations for all plasma, CVT, and CVF sample types, in addition to TFV-DP concentrations from CVT samples.

PD endpoints will be summarized using descriptive statistics by time point as well as changes from baseline. Estimates and 95% confidence intervals will be provided. Analysis will include summaries of anti-HIV and anti-HSV activity in CVF, and AUC (Area under the curve) and/or SOFT endpoints will be performed to determine if there is a difference between infection of samples collected at baseline and after treatment. Anti-viral activity in CVF (the change in HIV-1 and HSV infections for samples obtained on treatment vs. baseline) will be summarized.

Changes from baseline in clinical laboratory endpoints will be assessed using paired t test or Wilcoxon signed rank test based on the normality of the data. Repeated measures ANOVA or Friedman test for repeated measures will be used to assess the change from baseline through the endpoint.

Mixed effect-design will be used to compare within and between participants changes for different PK and PD endpoints from baseline to endpoint.

Disintegration and acceptability:

Disintegration endpoints will be summarized descriptively.

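### Comparability of the randomized arms is judged by baseline significance tests, which do not measure whether an imbalance matters; drop them and adjust suitable secondary comparisons for baseline and site

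*Protocol*

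**What the plan says.** Section 10.8.2, under descriptive statistics, sets the method for continuous baseline variables: "To assess for the comparability between the two arms of the study at baseline, t-test or Mann-Whitney test will be used". The next sentence covers the rest: "While chi-squared test for independence or Fisher's exact test will be used for categorical variables as appropriate". The stated purpose is comparability of the arms, not an audit of the randomization procedure. No significance level is given for these tests, no list of variables, and no action to follow a significant result.

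Section 10.5 forms the arms by chance: "Participants will be randomized (1:1) to receive either combination TAF/EVG or placebo vaginal insert". Section 6.1 says that this is done at each site.

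Two analyses in section 10.8.3 compare the arms after dosing. For binary adverse-event outcomes, "then Multivariable logistic regression will be used to assess for the difference in the occurrence of TEAEs". For laboratory safety parameters, a mixed-effect analysis "will assess for the differences in the laboratory parameters between the TAF/EVG and placebo group". Section 10.8.3 does not mention the baseline tests.

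**The concern.** Under sound randomization the null hypothesis of each baseline test is true by design. A significant result is a chance difference, and a non-significant one does not make an observed imbalance harmless. What matters is the size of the observed imbalance and how strongly the variable predicts the outcome. A p-value gives neither.

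Followed as written, the report would call the arms comparable or not on these p-values. In a 60-woman safety study whose objectives are judged by clinical review of summaries, a chance flag could be used to discount a safety signal, and a set of non-significant tests could reassure without cause. The section also leaves room for a better use of the baseline data: as prespecified covariates in the secondary between-arm comparisons.

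**Working it through.** **Number of women (section 10.4).** The only design figure is "difference at 5% level of significance and 80% power is 20 (10 participants in each arm) per site for a total of 60 participants", for a difference of 60% or more. I read this as 60 percentage points and use n per arm = [1.960·√(2p̄(1−p̄)) + 0.842·√(p₁(1−p₁)+p₂(1−p₂))]² / (p₂−p₁)². For 0.20 v 0.80 this is (1.386 + 0.476)²/0.36 = 9.6, so 10. Placebo rates from 0 to 0.40 (none is stated) give 8 to 10. The stated 10 per arm per site is reproduced, which makes 30 per arm overall.

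**What a t-test can flag.** It is significant at 5% when the observed standardized difference exceeds t(0.975; 2n−2)·√(2/n).
- 30 v 30: 2.002 × √(2/30) = 0.52 SD.
- 10 v 10 (within one site): 2.101 × √(2/10) = 0.94 SD.

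Smaller observed differences pass, however prognostic the variable.

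**Chance flags.** With k independent variables tested at 5%, P(at least one) = 1 − 0.95^k. Both k and the 5% level are assumptions.

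| k | P(at least one) | Expected number |
|---|---|---|
| 5 | 23% | 0.25 |
| 10 | 40% | 0.50 |
| 15 | 54% | 0.75 |
| 20 | 64% | 1.0 |

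Positively correlated variables would usually lower the middle column. The expected number would not change.

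**Non-significant is not harmless.** A simulation used 20,000 runs, 30 per arm, no treatment effect and a covariate with assumed correlation 0.7 with the outcome. Where the baseline p lay between 0.05 and 0.20, the unadjusted outcome comparison rejected in 11% of runs. Over all runs it rejected in 4.9%. There is no overall inflation, but in those trials the test result would have hidden a relevant imbalance.

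**What baseline adjustment offers.** Take a continuous outcome, 30 per arm, a true difference of 0.6 SD, equal variance before and after dosing, and correlation ρ between the two. The standardized effects are:
- unadjusted: 0.6
- change score: 0.6/√(2(1−ρ))
- adjusted for baseline: 0.6/√(1−ρ²)

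| ρ | Unadjusted | Change score | Baseline-adjusted |
|---|---|---|---|
| 0.4 | 0.60 → 63% | 0.548 → 55% | 0.655 → 70% |
| 0.6 | 0.60 → 63% | 0.671 → 72% | 0.750 → 81% |

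Power is from the noncentral t distribution at two-sided 5% (58 degrees of freedom, or 57 with adjustment). Any gain from site is not included.

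**Which endpoints have a pre-dose value (Appendix I and Table 9).** Clinical laboratory parameters are measured at screening. CVF anti-HIV and anti-HSV activity, soluble markers and Nugent score are measured at Visits 2 and 3. IHC biopsies are taken at Visit 2. Plasma and tissue PK have no pre-dose sample. Ex vivo p24 biopsies are taken at EVMS only.

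**The case against.** The strongest reply is that little depends on these tests. The primary endpoint is binary, is compared by an unadjusted chi-squared or Fisher test, and is judged alongside descriptive review. No baseline p-value can change that result. This stands.

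A reader might infer that a significant baseline test decides which covariates enter the models of section 10.8.3, and that power is lost in that way. The document does not support this. It gives no such rule, and leaving covariates unnamed is something a protocol may leave to the statistical analysis plan. The power gap in the table is the difference between unadjusted or change-score analysis and baseline-adjusted analysis. The tests do not cause it, and deleting them alone would not recover it.

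It is also fair to say that section 10.8.3 already plans mixed-effect models and changes from baseline, so own-baseline values enter several analyses in some form. The unadjusted 63% is then not the right comparator everywhere, which is why the change-score range is shown.

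A much higher chance of a false flag, such as 79% for 30 variables, could be built by counting every marker. But the protocol lists no variables for testing, many markers are given only as examples, and they are unlikely to be independent.

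Finally, adjusting every quantitative endpoint for baseline and site cannot be done: some have no pre-dose sample and one is collected at a single site.

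**Conclusion.** The concern holds in limited form. Section 10.8.2 prescribes an unsuitable method for its stated purpose, and nothing elsewhere in the protocol withdraws it. Within a t-test, observed differences below about 0.52 SD at 30 v 30 are passed as comparable, and 23% to 64% of sound randomizations would show at least one flag. That range assumes 5 to 20 independent variables tested at 5%.

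The harm is confined to the comparability statement and to the secondary analyses. The primary comparison is unaffected, no test-then-adjust rule is stated, and no overall type I error inflation is shown.

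Prespecified adjustment is a separate, free improvement: about 70% to 81% power against 63% unadjusted or 55% to 72% with change scores. It rests on an assumed effect of 0.6 SD, a correlation of 0.4 to 0.6, a continuous outcome and 30 women per arm.

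**What to change.** In section 10.8.2, delete the baseline t, Mann-Whitney, chi-squared and Fisher comparisons. Tabulate baseline values by arm without p-values.

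In section 10.8.3:
- For between-arm comparisons of quantitative endpoints with a scheduled pre-dose value (clinical laboratory parameters, CVF anti-HIV and anti-HSV activity, soluble markers, IHC markers, Nugent score), adjust for the woman's own baseline value and for site, whatever imbalance is seen.
- Omit the baseline term where no pre-dose sample exists (plasma and tissue PK), and omit site for the single-site p24 endpoint.
- State that covariates, including those in the logistic models, are not chosen from baseline tests.

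The cost is wording in two subsections. Sample size, visits and specimens stay as they are. All that is lost is the p-value column of the baseline table.

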10.8.3 Secondary and Exploratory Analyses

Safety:

To assess for the difference in subclinical safety endpoints between TAF/EVG and placebo group, the incidence of different TEAES will be calculated and risk ratio will be estimated. Chi-squared test or fisher exact test will be used as appropriate. A binary variable will be created for each one of the TEAEs of interest, then Multivariable logistic regression will be used to assess for the difference in the occurrence of TEAEs. In this model the risk ratio will be calculated instead of the odds ratio using Stata command (*oddrisk*).

While for quantitative laboratory safety parameters, mixed-effect design will be used to assess for the changes in these parameters over time within the TAF/EVG and placebo group separately

and will assess for the differences in the laboratory parameters between the TAF/EVG and placebo group.

PK and PD:

PK analysis will include descriptive statistics by sample time point of EVG, TFV, and TAF concentrations for all plasma, CVT, and CVF sample types, in addition to TFV-DP concentrations from CVT samples.

PD endpoints will be summarized using descriptive statistics by time point as well as changes from baseline. Estimates and 95% confidence intervals will be provided. Analysis will include summaries of anti-HIV and anti-HSV activity in CVF, and AUC (Area under the curve) and/or SOFT endpoints will be performed to determine if there is a difference between infection of samples collected at baseline and after treatment. Anti-viral activity in CVF (the change in HIV-1 and HSV infections for samples obtained on treatment vs. baseline) will be summarized.

Changes from baseline in clinical laboratory endpoints will be assessed using paired t test or Wilcoxon signed rank test based on the normality of the data. Repeated measures ANOVA or Friedman test for repeated measures will be used to assess the change from baseline through the endpoint.

Mixed effect-design will be used to compare within and between participants changes for different PK and PD endpoints from baseline to endpoint.

Disintegration and acceptability:

Disintegration endpoints will be summarized descriptively.

Acceptability endpoints will be summarized by assessment time point using descriptive statistics (e.g., frequencies, means), as appropriate. We will compare ratings of key acceptability measures over time (e.g., after initial insertion and after actual use), assessing whether they changed with increased experience with product insertion using a one-sample t test. In addition, analyses will examine sociodemographic and behavioral correlates of acceptability endpoints using linear regression models with robust standard errors (for rating outcomes) and using multivariable logistic regression for dichotomous outcomes such as willingness to use (e.g., disinterest in future use).

Qualitative Analysis:

Qualitative analyses from the MATRIX 001 study will use a variety of techniques to provide an in-depth characterization of the contextual factors that affected participants' product preferences. The primary source of qualitative data used in the analysis will consist of raw textual data. Qualitative data will be audio-recorded, translated and transcribed in English, and coded for thematic analyses using Dedoose or a similar qualitative software. Data coding will be used as a primary analytical approach for data reduction; that is, to summarize, extract meaning, and condense the data. Whenever possible, we will also compare study sites and explore differences or similarities related to product preferences due to different socioeconomic, cultural and geographical contexts. The findings and interpretations of the data will be critically discussed until there is group consensus on the dominant themes and meanings contained in the data. Whenever possible, site staff will be involved to corroborate findings from the analysis team.

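### Converting each TEAE model's odds ratio to a risk ratio can exaggerate the effect and its precision when events are common and risk is higher on active; estimate the risk ratio directly

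*Protocol*

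**What the plan says.** Under Safety, Protocol section 10.8.3 first plans incidences by arm with an unadjusted risk ratio, and adds "Chi-squared test or fisher exact test will be used as appropriate". It then goes further: "A binary variable will be created for each one of the TEAEs of interest, then Multivariable logistic regression will be used". Of this model it says "In this model the risk ratio will be calculated instead of the odds ratio using Stata command", and it names the command.

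The protocol therefore fixes three things: the model, the conversion of its odds ratio, and the software step. It does not state the conversion formula, the covariates, how an interval would be obtained, or what happens when an arm has no events.

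Two other places give the setting. Section 10.4 plans 10 women per arm at each of three sites, and section 10.5 shows 30 per arm. Section 2.5.2 reports the earlier single-dose study of 16 women: any TEAE in 7, the most common single TEAE in 3, and otherwise "No other TEAE occurred in more than 1 participant".

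**The concern.** An odds ratio can be turned into a risk ratio only by way of a baseline risk. Doing this after a multivariable fit raises two problems.

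- **Point estimate.** The adjusted odds ratio is conditional on the covariates. If it is combined with a single overall placebo risk, it does not in general return the overall risk ratio when risk varies across covariate levels.
- **Interval.** Passing the odds-ratio limits through the formula treats the placebo risk as known, although it is estimated from about 30 women.

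Both matter most when a TEAE is more frequent on active, which is the direction a safety comparison exists to detect. A third problem is separate: rare TEAEs may leave an arm with no events, so that the model has no finite treatment coefficient.

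**Working it through.** **Inputs from the protocol.** 30 per arm, 10 per arm at each of three sites (10.4, 10.5). Earlier TEAE rates: 7/16 = 43.8% for any TEAE, 3/16 = 18.75% for the most common one, at most 1/16 = 6.25% for every other (2.5.2).

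**Assumptions.** Conversion RR = OR/((1-P0) + P0 x OR), with P0 the overall placebo risk; site as the covariate, because 10.4 foresees an analysis by site. The protocol states neither.

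**Plan's own figure.** No figure is attached to this analysis. The sample size does reproduce if the 60% difference means percentage points and the test is two-sided. For 80% versus 20%, n = [1.96 x sqrt(2 x 0.25) + 0.842 x sqrt(0.16 + 0.16)]^2 / 0.36 = 9.6, so 10 per arm.

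**1. Bias of the converted risk ratio.** This is a large-sample logistic fit on arm and site, with a true risk ratio of 2.0 at every site.

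| Site placebo risks | P0 | Adjusted OR | Converted RR | Error |
|---|---|---|---|---|
| 2/6/11% | 6.3% | 2.21 | 2.05 | +2% |
| 10/19/28% | 19.0% | 2.79 | 2.08 | +4% |
| 10/20/40% | 23.3% | 3.58 | 2.24 | +12% |
| 5/20/45% | 23.3% | 4.55 | 2.49 | +24% |

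Last row: 4.55/(0.767 + 0.233 x 4.55) = 4.55/1.828 = 2.49. With equal site risks, or no effect, the error is nil. If the odds ratio rather than the risk ratio is held constant across sites (OR 2 to 4), the error is +2% to +5% at 2/6/11%, +5% to +7% at 10/20/40% and +10% to +16% at 5/20/50%.

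**2. Width of the converted interval.** With P0 fixed, the derivative of log RR with respect to log OR is 1 - p1, where p1 is the active risk. The implied standard error is therefore (1 - p1) x SE(log OR). The correct one is sqrt[(1-p0)/(30 p0) + (1-p1)/(30 p1)].

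At 18.75% versus 37.5%:
- SE(log OR) = sqrt(1/5.625 + 1/24.375 + 1/11.25 + 1/18.75) = 0.601
- converted: 0.625 x 0.601 = 0.376
- correct: sqrt(0.1444 + 0.0556) = 0.447
- ratio: 0.84

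The same ratio is 0.81 at 30% versus 50%, 1.00 with equal arms, and 1.04 (slightly too wide) at 18.75% versus 10%.

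Coverage of the 95% interval, unadjusted, 30 per arm:

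| Placebo vs active | Converted OR limits | Direct RR |
|---|---|---|
| 18.75% vs 37.5% | 90% | 97% |
| 30% vs 50% | 88% | 96% |
| 44% vs 70% | about 80% | 95% |
| 44% vs 44% | 95% | 95% |

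At about 6.25% placebo risk with OR 2 to 4, simulated coverage of the converted interval, among trials that gave an estimate, was 94% to 98%.

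**3. Empty arms.** With risk p in both arms, let z = (1-p)^30. At least one arm is empty with probability 2z - z^2.

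- 6.25%: z = 0.144, probability 27% (3.8 events expected in 60 women)
- 5%: 38%
- 2%: 79%
- 18.75%: 0.4%

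With an empty arm, the log odds ratio and the log risk ratio are both infinite, so this problem is not caused by the conversion.

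**The case against.** The strongest reply has four parts.

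- **The key inputs are assumed.** The protocol names no covariates, no formula and no interval for this risk ratio; in 10.8.3 a 95% interval is mentioned only for PD. Covariates and sparse-data rules may properly sit in the SAP. This stands, and it makes the sizes above conditional. It does not remove the point, because the model and the conversion are themselves stated in the protocol.
- **The large errors need unusual conditions.** The +24% case implies a 90% active risk at one site. The 44% rate is the earlier rate for any TEAE, not for a single one. At the single-TEAE rates seen earlier, the bias is about 2% to 4% unless sites differ strongly. This stands. Those earlier rates do come from one dose in 16 women, against ten doses here, so they are a weak guide.
- **The failures do not coincide.** Bias and undercoverage need common events and a real effect; empty arms need rare events. A reader might infer that the converted risk ratios will generally be biased, too precise and often missing all at once. The calculations do not support that. Nor does a site with no events (62% of trials at 6.25%) mean there is no treatment estimate: if both arms have events, the treatment odds ratio can still be estimated.
- **Little rests on this analysis.** It is secondary, and an unadjusted risk ratio and a chi-squared or Fisher test stand beside it. This stands and limits the consequence.

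**Conclusion.** The point holds in a conditional form. Under the usual formula and adjustment for site, the converted risk ratio is pushed away from 1 when there is a real effect, the TEAE is common and risk differs by site. The error ranges from a few percent in moderate settings to 24% in an extreme one. If the limits are converted in the same way, coverage is about 80% to 90% where active risk clearly exceeds a placebo risk of about 19% or more. It is close to nominal or above with equal arms or at about 6% placebo risk. For TEAEs at 6.25% or less per arm, an empty arm defeats both this method and a directly estimated risk ratio in at least 27% of trials.

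A reader might conclude that the trial's safety finding is at risk. The protocol does not support that: the primary TEAE comparison in 10.8.2 uses chi-squared or Fisher, and the unadjusted risk ratio in 10.8.3 needs no conversion. The case for change is that the conversion adds avoidable error, chiefly when there is excess risk on active, and offers nothing that direct estimation does not.

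**What to change.** In 10.8.3, replace the odds-ratio conversion with a directly estimated risk ratio and its interval. Use either a log-link Poisson model with robust variance, or marginal standardization after the logistic fit, adjusted for site. For TEAEs too sparse for a model, report counts by arm and a risk difference with an exact or score interval, and fit no multivariable model. The event count that separates the two cases can be set in the SAP before unblinding.

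The cost is a change of wording and the use of standard commands; design, sample size and data collection stay the same.
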